Study Title: Impact of Sleep Restriction on Cardiometabolic Risk Factors in Pre- and Postmenopausal Women

Short Title: Impact of Sleep Restriction in Women

ClinicalTrials.gov ID: NCT02835261

Document Date: 2016 February 16 (original); 2020 July 21 (final revision); 2025 October 09

(submitted)

SPECIFIC AIMS

The overall goal of this project is to test the hypothesis that long-term, sustained SR, in women, will lead to increased cardio-metabolic risk. This will be characterized by increases in visceral adiposity, unhealthy lifestyle behaviors (poor dietary quality and low physical activity) and cardio-metabolic risk factors (blood pressure, glucose intolerance) relative to HS. We expect these changes to be worse in pre- compared to post-menopausal women.

Specific Aim 1. To assess the effects of SR on cardio-metabolic risk profile, relative to HS.

Hypothesis 1: Prolonged SR will lead to increased blood pressure and reduced glucose tolerance relative to HS.

Specific Aim 2. To assess the effects of SR on adiposity, relative to HS, over a 6-week period. *Hypothesis 2:* Prolonged SR will lead to increased visceral adiposity, assessed by magnetic resonance imaging (MRI), relative to HS.

Specific Aim 3. To assess the effects of SR on diet and physical activity level.

Hypothesis 3a: Prolonged SR will lead to reduced physical activity relative to HS.

Hypothesis 3b: Diet quality will be reduced with SR relative to HS, as reflected by increased intake of snacks, fat, and simple sugars.

Exploratory Hypothesis: The effects of prolonged SR on adiposity and cardio-metabolic risk factors will be greater in pre-menopausal women relative to post-menopausal women.

RESEARCH DESIGN & METHODS

Study population & Sample size determination

We will enroll 80 participants and expect 50 to complete the study. This drop-out rate accounts for participant non-compliance and withdrawal from the study. In our previous *Sleep Study*, our completion rate was 90% (27/30). We expect a larger drop-out rate in the proposed study due to the longer duration of each treatment phase, and also, some participants may be dismissed from the study from their inability to achieve and maintain the 1.5 h average weekly SR.

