In this proposed study, each participant will undergo 2 study phases, and each response variable will be measured *at least* once per phase. Thus, for each response measure we will have at least 50×2 paired observations. Based on preliminary data analysis, we have estimated an effect size (mean paired difference) of 0.69 ± 0.36 g for fat mass and an effect size (mean paired difference) of 0.91 ± 0.65 g for weight gain. This translates to very large effect sizes of 1.92 (fat mass) and 1.4 (weight gain) for paired t-tests. With these effect sizes we will have >80% power for paired t-tests with our expected sample size and will have sufficient power to test for differences between pre- and post-menopausal women.

Eighty pre- and postmenopausal women, age 20-65 y i with an overweight BMI (25-29.9 kg/m²) ii will be recruited from the New York City area. These women will come from the pool of participants in the Population Science project in this Center application. Pre-menopausal women will not be on oral contraceptive medications and post-menopausal will not be on hormone replacement therapy. In addition, women recruited to participate in this study will habitually sleep 7-9 h/night, will be free of any current and past sleep and psychiatric disorders, including eating disorders (ex. anorexia, bulimia, night eating syndrome), and will not have type 2 diabetes or CVD (**Table 2**) iii. We will exclude women taking medication to reduce blood pressure and cholesterol levels. Smokers (defined as currently smoking any cigarettes or ex-smokers <3 y), non-day and rotating shift workers, persons who plan to travel across time zones within 4 weeks of the study, and those with a history of drug and alcohol abuse, drowsy driving, or excessive caffeine (>300 mg/d) or alcohol intakes >2 drinks/day) will also be excluded. Further, we will not enroll women who have had a recent weight change or who actively participated in a diet or weight loss program in the previous 3 mo, and those with a neurologic condition that may disrupt the procedures. Women who are pregnant or <1 y post-partum, and those with contraindications for MRI scanning will be excluded iv. All participants will have normal scores on the

ⁱ See Amendment 1b

ii See Amendment 1c

iii See Amendment 1d

iv See Amendment 1a

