This study will be a randomized, crossover, outpatient SR study with 2 phases of 6 weeks each. Sleep duration in each phase will be the participant's regular bed- and wake-times during the HS phase and HS minus 1.5 h in the SR phase. During the HS phase, participants will be asked to follow a fixed bedtime routine based on their screening sleep schedule. During the SR phase, participants will be asked to keep their habitual wake time constant but delay their bedtime to achieve a reduction of 1.5 h in total sleep time. A delay in bedtimes was chosen rather than advancing wakeup time because it likely most closely reflects differences in sleep timing behavior between short and normal sleepers. Spaeth and colleagues have also shown that restricting sleep to the latter portion of the night is associated with increased food intake and weight gain relative to HS (8). We also considered providing fixed bed- and wakeup times for all women but decided to provide individualized bedtimes and wakeup times to reduce variability in our sample.

On the first day of each study phase (baseline), participants will come to the Clinical Research Resource (CRR) of the Irving Center for Clinical and Translational Research (CTSA) at CUMC in the morning after an overnight, 12 h fast. Participants will have anthropometric measurements taken and will then be taken to the department of Radiology to undergo magnetic resonance imaging (MRI) scanning to assess body composition. They will then return to the CRR for an oral glucose tolerance test. Participants will begin the fixed bedtime routine that night. These baseline measurements will be

repeated at endpoint, 6 weeks later. Body weight and waist circumference will be measured weekly and fasting blood samples will be taken bi-weekly during adherence check visits v.

Recruitment and blinding

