Linear Mixed Model Analyses. We will fit a linear mixed model to analyze the data. Treatments (sleep: SR vs. HS) will be used as fixed effects and subject will be used a random effect. The other independent variables (covariates) will be age, baseline BMI, and race/ethnicity. If required anywhere in the analysis plan, p-values will be adjusted for multiple comparisons.

Specific Aim 1. To assess the effects of SR on cardio-metabolic risk profile, relative to HS. (Hypothesis 1: Prolonged SR will lead to increased blood pressure and reduce glucose tolerance relative to HS.) We will perform a repeated measure linear mixed model analyses separately with each of blood pressure and glucose tolerance measures (each in a separate model) as the response and sleep (SR vs. HS), time, sleep-time interaction and the covariates as independent variables, with data from all time points combined. Subject will be used as a random effect. Additionally, we will also use the change from baseline to week-6 in each of blood pressure and glucose tolerance measures as response variables in separate regressions, where sleep (SR vs. HS) and the covariates will be used as the independent variables. Paired one-sided t-test and Wilcoxon test will be used to determine whether the SR is associated with increased blood pressure and reduced glucose tolerance vs. HS.

Specific Aim 2. To assess the effects of SR on adiposity, relative to HS, over a 6-week period. (Hypothesis 2: Prolonged SR will lead to increased visceral adiposity, assessed by MRI, relative to HS.) We will perform a repeated measure linear mixed model analyses separately with each visceral adiposity variable (as observed by MRI) (each in a separate model) as the response and sleep (SR vs. HS), time, sleep-time interaction and the covariates as independent variables, with data from all time points combined. Subject will be used as a random effect. Additionally, we will also use the change from baseline to week 6 in each adipose tissue variable as response variables in separate regressions, where sleep (SR vs. HS) and the covariates will be used as the independent variables. Paired one-sided t-test and Wilcoxon test will be used to determine whether the SR is associated with increased adiposity variable relative to HS.

_

xiii See Amendment 2a

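### The additional change-from-baseline regressions in Aims 1–3 name no subject term; as most naturally read, they treat each woman's two phase changes as independent, which misstates the SR–HS standard error unless those changes are uncorrelated

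*Combined protocol and SAP*

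**What the plan says.** The Overview of study design states: "This study will be a randomized, crossover, outpatient SR study with 2 phases of 6 weeks each". Under Study population & Sample size determination, "We will enroll 80 participants and expect 50 to complete the study", and "for each response measure we will have at least 50×2 paired observations".

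The Statistical analysis plan, under Linear Mixed Model Analyses, opens with a general paragraph. It announces a linear mixed model, says that "subject will be used a random effect", and defines the covariates as age, baseline BMI and race/ethnicity.

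The text for Aims 1, 2, 3a and 3b then has the same three steps each time:

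1. A repeated-measures mixed model with sleep, time, their interaction and the covariates, followed by a separate sentence making subject a random effect.
2. An additional analysis in which the baseline-to-week-6 changes are taken "as response variables in separate regressions, where sleep (SR vs. HS) and the covariates will be used as the independent variables". No subject term, within-woman covariance or clustered SE is attached.
3. Paired one-sided t-tests and Wilcoxon tests, given as the means of deciding whether SR has the hypothesised effect.

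The paragraph before Linear Mixed Model Analyses also puts a phase main effect into the initial version of every linear model and drops it if it is not significant.

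**The concern.** Pairing is the reason for running a crossover. If step 2 is carried out as ordinary regression, 50 pairs are analysed as about 100 unrelated rows. The residual variance then contains the between-woman variation that the design is meant to remove, or, if the two changes are negatively correlated, understates the variability of their difference.

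Two things are at stake:

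- **The SR–HS comparison.** The regression and the paired t-test on the same outcome could disagree on significance only because one ignores the pairing. The plan does not say which of its three analyses prevails.
- **The phase test.** Phase is also a within-woman contrast, so its SE in these regressions is wrong by the same factor. With positive correlation a real phase effect is more easily missed and removed from the model.

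**Working it through.** **Inputs from the documents.** Two phases per woman; 50 expected completers; preliminary paired differences given as "effect size (mean paired difference) of 0.69 ± 0.36 g for fat mass" and "effect size (mean paired difference) of 0.91 ± 0.65 g for weight gain"; and the statement "we will have >80% power for paired t-tests with our expected sample size".

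**Assumptions not in the documents.** α = 0.05; complete pairs; equal variance s² of the two changes; covariates constant within a woman; ρ, the correlation of the two changes left after the covariates, between −0.3 and 0.5.

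**The plan's own figure.**

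- Effect sizes: 0.69/0.36 = 1.92 and 0.91/0.65 = 1.40.
- Noncentrality with n = 50: 1.917 × √50 = 13.55 and 1.40 × √50 = 9.90.
- Paired-t power on 49 df exceeds 0.999 for both, one- or two-sided, so the claim of more than 80% is reproduced.

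This concerns paired t-tests on fat mass and weight, so it does not bear on the regressions. Nor does it yield ρ. The SD of a paired difference satisfies SD² = 2s²(1−ρ), and the plan gives no s.

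**Effect of leaving out subject.**

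- True variance of the SR–HS mean difference: 2s²(1−ρ)/n.
- Variance used by a regression without subject: about 2s²/n.
- Reported SE / true SE = r = 1/√(1−ρ).

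With n = 50 the reported SE is s√(2/50) = 0.200s whatever ρ is. The true SE is 0.200s × √(1−ρ).

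By normal approximation, the actual one-sided error rate is 1 − Φ(1.645r). Power, for an effect that has 80% power when the pairing is kept, is Φ(1.645 + 0.842 − 1.645r).

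| ρ | True SE | r | Actual one-sided error | Power instead of 80% |
|---|---|---|---|---|
| −0.3 | 0.228s | 0.88 | 7.5% | – |
| 0 | 0.200s | 1.00 | 5.0% | 80% |
| 0.3 | 0.167s | 1.20 | 2.5% | 70% |
| 0.5 | 0.141s | 1.41 | 1.0% | 56% |

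Worked row, ρ = 0.3: r = 1/√0.7 = 1.195; 1.645 × 1.195 = 1.966; Φ(2.487 − 1.966) = Φ(0.521) = 0.70.

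Two-sided, using 1.960 in place of 1.645, power is 68% at ρ = 0.3 and 51% at ρ = 0.5, and the error rate at ρ = −0.3 is 8.6%.

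**Check by simulation.** With 50 women, three woman-level covariates and 20,000 runs per value of ρ, the regression without subject gave two-sided error rates of 0.085 (ρ = −0.3), 0.050 (0), 0.020 (0.3) and 0.007 (0.5). The paired analysis gave 0.049 to 0.053 throughout.

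**The case against.** The strongest reply is that the plan never says the changes are independent. The general paragraph under Linear Mixed Model Analyses makes subject a random effect, and nothing confines it to the repeated-measures models. The change regressions rely on that paragraph for the definition of the covariates. A random effect need not be listed among independent variables: in the repeated-measures models it is not, and has its own sentence. Nor is the listed set of regressors exhaustive, because the phase term required in every linear model is missing from it too.

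This stands to the extent that the text is unclear rather than an explicit independence analysis. It does not remove the point. The subject sentence is repeated in every aim after the mixed model and never after the change regression, and the wording shifts from mixed model to regressions. An analyst following the text would most naturally omit subject. Even if the general paragraph applies, a random intercept whose variance cannot go below zero falls back to independence when ρ is negative; that is a secondary matter.

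A reader might also infer more than the documents support:

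- **That the aims rest on a wrong analysis.** They do not. The regressions are introduced as additional, and the mixed model and paired tests in the same aims account for subject.
- **That false positives are inflated.** This requires negative ρ. Positive ρ makes the regression conservative. Each phase has its own baseline after a washout of generally 6 weeks, so losing a phase 1 gain during washout does not in itself make ρ negative. Negative ρ is possible but not shown.
- **That the stated power fails.** It is a claim about paired t-tests, and it holds. The 80% starting point above is illustrative.

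**Conclusion.** The point holds as an unclear specification whose natural reading is an error. If subject is omitted, the SR–HS estimate remains unbiased with complete pairs, but its SE, and that of the phase term, is multiplied by 1/√(1−ρ). Over the assumed range this runs from 0.88 to 1.41, with no error at ρ = 0. The direction cannot be settled from the documents.

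The practical loss depends on the outcome. If the preliminary effect for weight held, ρ = 0.5 would reduce its noncentrality only from 9.90 to 9.90/1.414 = 7.00, which is immaterial. The loss matters for outcomes with modest effects. The plan gives no effect size for blood pressure, glucose tolerance, visceral fat, physical activity or diet.

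Severity is should-fix: only supplementary results and the phase test within them are affected.

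**What to change.** In the change-from-baseline sentences for Aims 1, 2, 3a and 3b, state that the analysis keeps the pairing, and choose one form:

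- **Difference regression.** One row per woman, with SR change minus HS change as the outcome and mean-centred covariates (indicator columns for race/ethnicity centred too). The intercept is then the average SR–HS effect; with uncentred covariates it would not be. Where phase is tested, include phase order coded +1/−1, so that the intercept keeps its meaning and the order coefficient estimates the phase effect.
- **Bivariate model.** Both changes per woman, with sleep, phase where tested, and covariates as fixed effects, and an unstructured 2×2 within-woman covariance. This allows correlation of either sign.

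If the general paragraph was meant to cover these regressions, say so and name the covariance structure. The cost is a sentence or two in the analysis plan. No new data or procedures are needed.

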an ELISA (R&D Systems, Inc., Minneapolis, MN), using 200 uL sera. The manufacturer indicates that the tumor necrosis factor-α assay has an approximate minimal detectable concentration of 0.12 pg/mL. Interleukin-6 will be assessed with an ELISA (R&D Systems, Inc., Minneapolis, MN) using 200 uL sera. High-sensitivity C-reactive protein will be assessed with an ELISA (ALPCO Diagnostics, Windham, NH). Serum samples will be diluted 1:100 prior to use. *Lifestyle behavior assessments*.

We will also assess physical activity level by waist actigraphy (GT3X+ Actigraph LLC, Pensacola, FL) throughout each study phase xiii. We hypothesize that total energy expenditure and physical activity level will be lower during the period of SR compared to HS.

Throughout the study, participants will self-select their food intake in a free-living situation. Food intake will be assessed at baseline and endpoint by 3-day food records (2 weekdays and one weekend day). Energy and macronutrient intakes from the food records will be assessed using the University of Minnesota Nutrition Data System for Research (NDSR, Minneapolis, MN).

Statistical analysis plan

Exploratory data analysis for all response variables will be performed using R, SAS and other software. As part of the analysis, we will compute descriptive statistics for each variable. In particular, the proportion, mean, variance, standard error and the range of continuous variables and frequency and model for discrete variables will be computed. Descriptive statistics will be computed for each specific sleep. In addition, correlation coefficients between the variables will be computed and scatter plots will be checked for linear relationships. The correlations and scatter plots help assess the degree of collinearity among the variables, which will be useful for the interpretation of regression-based linear mixed model analyses discussed later. The data will be tested for normality, and if needed an appropriate transformation will be used on the raw data to make the normal approximation better.

As we are collecting data from two phases for each subject, we will test for phase effect by using phase main effect term in an initial version of each linear model. If the term is not found to be significant then we will rebuild the linear model without the term.

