Specific Aim 3. To assess the effects of SR on diet and physical activity level. (Hypothesis 3a: Prolonged SR will lead to reduced physical activity relative to HS.) We will perform a repeated measure linear mixed model analyses separately with each physical activity measure (each in a separate model) as the response and sleep (SR vs. HS), time, sleep-time interaction and the covariates as independent variables, with data from all time points combined. Subject will be used as a random effect. Additionally, we will also use the change from baseline to week-6 in each physical activity measure as response variables in separate regressions, where sleep (SR vs. HS) and the covariates will be used as the independent variables. Paired one-sided t-test and Wilcoxon test will be used to determine whether the SR is associated with reduced physical activity measures relative to HS. (Hypothesis 3b: Diet quality will be reduced with SR relative to HS, as reflected by increased intake of snacks, fat, and simple sugars.) We will perform a repeated measure linear mixed model analyses separately with each diet quality measure (snacks, fat, and simple sugars intakes, each in a separate model) as the response and sleep (SR vs. HS), time, sleep-time interaction and the covariates as independent variables, with data from all time points combined. Subject will be used as a random effect. Additionally, we will also use the change from baseline to week-6 in each diet quality measure (snacks, fat, and simple sugars intakes) as response variables in separate regressions, where sleep (SR vs. HS) and the covariates will be used as the independent variables. Paired one-sided t-test and Wilcoxon test will be used to determine whether the SR is associated with reduced diet quality measure (i.e., increased snacks, fat, and simple sugars intakes) relative to HS.

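### Hypothesis 3b reads higher intakes of snacks, fat and simple sugars as lower diet quality, with no unit stated and no use of total energy, so eating more of an unchanged diet could be reported as reduced quality

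*Combined protocol and SAP*

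**What the plan says.** The Specific Aims and the Specific Aim 3 paragraph of the statistical analysis plan word Hypothesis 3b in the same way: "Diet quality will be reduced with SR relative to HS, as reflected by increased intake of snacks, fat, and simple sugars".

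The Aim 3 paragraph makes each of the three intakes the response in its own repeated-measures mixed model. It then uses the "change from baseline to week-6 in each diet quality measure (snacks, fat, and simple sugars intakes) as response variables" in separate regressions. One-sided paired t-tests and Wilcoxon tests are to show whether SR is associated with "reduced diet quality measure (i.e., increased snacks, fat, and simple sugars intakes) relative to HS".

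The paragraph on linear mixed models lists age, baseline BMI and race/ethnicity as the covariates. Energy intake is not among them.

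The data source is described under lifestyle behavior assessments: "Food intake will be assessed at baseline and endpoint by 3-day food records (2 weekdays and one weekend day"), and "Energy and macronutrient intakes from the food records will be assessed using the University of Minnesota Nutrition Data System for Research". Neither place states whether intake is expressed in grams, kilocalories, servings, per 1,000 kcal or as a percentage of energy. No diet-quality index is named.

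The Overview of study design cites an outside study in which "restricting sleep to the latter portion of the night is associated with increased food intake and weight gain relative to HS". The blinding text also gives altered food intake and resulting weight gain as reasons for concealing the study's purpose.

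**The concern.** The hypothesis is about quality, but the measures, on their natural reading, are quantities. When someone eats more of everything in the same proportions, fat, sugar and snack intakes all rise and the mix does not change. The stated tests would count that as evidence of lower quality. The opposite error is also possible: a worse mix within a lower total intake could go undetected.

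The design does not remove the problem. A crossover cancels stable differences between women, but a rise in total intake under SR is a within-woman treatment effect. Neither baseline BMI nor the other two covariates adjust for it. The sleep-by-time term in the mixed model picks up the same rise as the change analysis.

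At stake is what a positive 3b result can be said to show: that women ate more, that they ate a poorer mix, or both. The plan as written cannot tell these apart.

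**Working it through.** **The plan's own figure.** There is none for diet. The stated power above 80% rests on fat mass (0.69/0.36 = 1.92) and weight gain (0.91/0.65 = 1.40). With 50 pairs, both effect sizes give power above 99.9% at an assumed 5% level, so the statement holds. It has no bearing on 3b.

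**Inputs**
- From the document: 50 completers ("We will enroll 80 participants and expect 50 to complete the study"), a one-sided paired test, and the change from baseline to week 6 compared between SR and HS.
- Assumed, because the document gives no value: 2000 kcal/day, 35% of energy from fat, 9 kcal per g of fat, a 5% or 10% rise in energy with the same composition, a 5% test level, and an SD of 20 to 50 g for the paired difference in change.

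**Step 1. Shift in fat intake with composition unchanged**
- Before: 2000 × 0.35 / 9 = 77.8 g/day.
- After a 10% rise: 2200 × 0.35 / 9 = 85.6 g/day, a shift of +7.8 g.
- After a 5% rise: 2100 × 0.35 / 9 = 81.7 g/day, a shift of +3.9 g.
- Fat stays at 35% of energy throughout. Sugars and snacks rise by the same percentage.

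**Step 2. How often the test is significant.** The noncentrality is shift / SD × √50, with 49 degrees of freedom and a one-sided 5% critical value of 1.677. For example, 7.78 / 20 × 7.07 = 2.75.

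| SD of paired difference in change | 10% rise | 5% rise |
|---|---|---|
| 20 g | 0.857 | 0.386 |
| 30 g | 0.565 | 0.229 |
| 40 g | 0.386 | 0.167 |
| 50 g | 0.288 | 0.135 |

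**Step 3. Which SD is plausible.** Each paired difference, (SR week 6 − SR baseline) − (HS week 6 − HS baseline), uses four 3-day records. If record errors are independent with equal SD, its SD is √4 = 2 times the per-record SD.
- An SD of 20 to 30 g implies a per-record variation of 10/77.8 = 13% to 15/77.8 = 19%.
- A per-record variation of 20% to 30% (also assumed) gives 2 × 0.20 × 77.8 = 31 g to 2 × 0.30 × 77.8 = 47 g. Rejection is then about 54% to 31% for a 10% rise and 22% to 14% for a 5% rise.

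**Step 4. Check by simulation.** The setting was 4,000 runs, 50 women, per-record variation of 20% or 30%, only the SR week-6 record scaled up, and composition unchanged on average.

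| Rise in energy | Each outcome, absolute | At least one of three, absolute | Each outcome, energy-relative |
|---|---|---|---|
| none | about 5% | about 13% | about 5% |
| 5% | 14–21% | 31–44% | about 5% |
| 10% | 29–49% | 56–78% | about 5% |

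The column for at least one of three should be read against the 13% that arises from three unadjusted tests with no rise at all.

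**The case against.** **The unit is not stated.** Percent of energy is not expressly excluded, so it would go too far to say the plan demonstrably uses the wrong measure. This stands, and it is why the point is conditional on intake meaning amount. If an energy-relative measure was intended, the plan needs to say so.

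**The hypothesis defines its own construct.** Reduced quality is declared in advance to be reflected by increased intakes, and the tests match that definition. A reader might infer that a positive result would not answer 3b at all. The document does not support that: it would answer 3b as worded. Absolute intakes can also matter for adiposity and cardio-metabolic risk. What remains is that the word quality invites a conclusion the measures cannot isolate.

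**Unchanged composition is only a scenario.** A reader might infer that the protocol expects the very situation in which the rule fails. It does not. It cites one study of higher food intake to support delaying bedtime, says that food intake may alter, states no hypothesis on total energy and nowhere predicts an unchanged mix. Proportional scaling is least natural for snacks, since added snacking would change the mix. The scenario is possible on the protocol's own rationale, and no more is claimed.

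**The rejection rates rest on assumed inputs.** This also stands. The 86% figure needs an SD that is optimistic for a difference of two changes, and should not be quoted alone.

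**Conclusion.** The point holds in conditional form. On the natural reading of intake as amount, the 3b decision rule cannot separate eating more from eating a poorer mix, and the plan leaves unused the energy data that could separate them. With unchanged composition, a 10% rise in energy would give a significant fat result in about 86% to 29% of trials over SDs of 20 to 50 g, and a 5% rise in about 39% to 14%, against a nominal 5%. If each 3-day record varies by 20% to 30%, the lower part of each range applies. The direction follows from the definition of the measures; the rates depend on the assumed diet, variability, rise in energy and test level.

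The scope is limited to the interpretation of one sub-hypothesis of Aim 3. Nothing in Aim 1, Aim 2 or the power statement changes. It is worth correcting because dietary quality is part of the study's stated overall goal and no new data are needed.

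**What to change.** In the Specific Aim 3 paragraph of the statistical analysis plan:

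1. State the unit of each intake. Keep the absolute intakes as planned, labelled as intake (quantity).
2. Add total energy, fat and simple sugars as a percentage of energy, and snacks as a percentage of daily energy, using the same models and tests.
3. State that reduced diet quality will be concluded only when the energy-relative measures support it. A rise in absolute intakes alone is reported as higher intake.
4. If outcome data have already been analysed, label the added measures as not prespecified. The document's final revision is dated 2020 and its amendments describe accrued participants in the past tense, so this may apply.

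**Cost.** No new data collection: energy and macronutrients already come from the food records, and sugars and snacks are already planned outcomes. There are a few more analyses to report. Energy-relative shifts may be smaller than shifts in grams. A share can also move because another energy source changes, which is a reason to show absolute intakes, total energy and shares side by side.
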